We developed our research protocol to ensure an adequate sample size for statistical analyses. We used previous data to calculate statistical power for biomechanical and metabolic variables using G*Power statistical software [25]. We set $\alpha = 0.05$, had a sample

size of 30, and used a paired t-test design. We used data from D'Andrea et al. [14] who compared peak vertical GRFs, peak horizontal GRFs, and sagittal plane H range during walking at 0.75-1.75 m/s for eight participants with unilateral TTAs using a passive-elastic prosthesis compared to a powered ankle-foot prosthesis. We calculated symmetry indices (SI) for these biomechanical variables and found strong statistical power (>0.689) for detecting differences in the first peak vertical GRF and strong statistical power (>0.717) for detecting differences in the peak horizontal braking and propulsive GRF in subjects using their own passive-elastic prosthesis compared to the BIOM battery-powered ankle-foot prosthesis (Table 1). The second peak vertical GRF and sagittal plane H had strong statistical power (1.0) at 1.75 m/s, but moderate to low power at the other walking speeds. Further we used data from Herr & Grabowski [11] to determine the statistical

Table 1. Statistical Power for variables reported by previous studies from 0.75-1.75 m/s.

Variable	Statistical Power
SI 1 st peak vertical GRF	0.689-1.0 [14]
SI 2 nd peak vertical GRF	0.249-1.0 [14]
SI Peak horizontal braking GRF	0.996-1.0 [14]
SI Peak horizontal propulsive GRF	0.717-1.0 [14]
SI Sagittal Plane H range	0.115-0.95 [14]
UL Leading/AL Trailing Leg Mechanical Work	1.0 [11]
Metabolic Cost (0.75-1.75 m/s)	0.655-1.0 [11]

power for UL leading leg and AL trailing leg mechanical work and metabolic cost between subjects using their own passive-elastic prosthesis compared to the BiOM battery-powered ankle-foot prosthesis across five walking speeds (0.75-1.75 m/s). We found strong statistical power (1.0) to detect differences in mechanical work and metabolic cost at 1.0-1.75 m/s (Table 1).

G. Summarize Knowledge to be Gained:

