Specific Aim 1. Determine the biomechanics and metabolic costs of level-ground walking for 30 Veterans with unilateral TTAs using their own passive-elastic prosthesis both with and without visual feedback training. Each subject will walk at 1.25 m/s on a dual-belt force-measuring treadmill while they use their own passive-elastic prosthetic foot: 1) with no visual feedback, and then with real-time visual feedback targets of: 2) peak propulsive force from the "no feedback" condition, 3) +20% greater peak propulsive force, and 4) +40% greater peak propulsive force. During these visual feedback trials (2-4), we will ask subjects to match the peak propulsive force displayed on a computer monitor (Fig. 1) with their affected leg (AL). We will also ask subjects to: 5) match symmetric visual feedback of the peak propulsive force from both legs. **Hypothesis 1a:** Because passive-elastic prosthetic feet cannot generate power *de novo*, Veterans with TTAs using such prostheses will adopt compensatory biomechanics in their AL and/or unaffected leg (UL) to match the +20% and +40% greater peak propulsive force conditions with their AL and symmetric peak propulsive forces in both legs when using visual feedback during walking, which will increase asymmetry in other values between legs and worsen dynamic stability. Examples of compensatory biomechanics include greater positive joint work and peak joint power in the AL hip joint and/or UL ankle, knee, and hip joints. **Hypothesis 1b:** Due to the negative relation between peak propulsive force and metabolic cost, the metabolic cost of walking when using a passive-elastic prosthesis will be lowest when subjects use visual feedback of +40% peak propulsive force compared to all other conditions. **Hypothesis 1c:** After a 5-min rest period, subjects using their own passive-elastic prosthetic foot will not retain the biomechanics resulting from the prior visual feedback conditions due to compromised stability.

Specific Aim 2. Determine the biomechanics and metabolic costs of level-ground walking for 30 Veterans with unilateral TTAs using a battery-powered ankle-foot prosthesis both with and without visual feedback training. Each subject will walk at 1.25 m/s on a dual-belt force-measuring treadmill while they use a battery-powered ankle-foot prosthesis (emPOWER, BiONX, Ottobock):

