1) with no visual feedback, and then with real-time visual feedback targets of: 2) peak propulsive force from the “no feedback” condition, 3) +20% greater peak propulsive force, and 4) +40% greater peak propulsive force. During these visual feedback trials (2-4), we will ask subjects to match the peak propulsive force displayed on a computer monitor (Fig. 1) with their AL. We will also ask subjects to: 5) match symmetric visual feedback of the peak propulsive force from both legs. **Hypothesis 2a:** Because the emPOWER generates stance-phase prosthetic ankle joint power and net positive work, Veterans with TTAs using the battery-powered prosthesis will be able to match the +20% and +40% greater peak propulsive force conditions with their AL and symmetric peak propulsive forces in both legs without requiring compensatory biomechanics when using visual feedback during walking, which will improve symmetry between legs and dynamic stability. **Hypothesis 2b:** Due to the negative relation between peak propulsive force and metabolic cost, the metabolic cost of walking when using a powered ankle-foot prosthesis will be lowest when subjects use visual feedback of +40% peak propulsive force compared to all other conditions. **H2c:** After a 5-min rest period, subjects will retain the biomechanics resulting from the visual feedback conditions due to improvements in symmetry, metabolic costs, and stability. **Hypothesis 2d:** Veterans with TTAs will have more symmetric biomechanics, lower metabolic costs, and improved dynamic stability when using powered compared to passive-elastic prostheses across all conditions.

II. Background and Significance:

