Days 2, 3 and 4 – Experimental Sessions. We will ask subjects to fast and drink nothing but water for at least 2 hours prior to each experimental session. On each day, we will attach reflective motion capture markers to their legs and pelvis using double-sided tape and Velcro straps, and surface electrodes over their leg muscles using double-sided tape and elastic wraps. We will mark the locations of each electrode with "permanent" marker on their skin. Then, we will ask subjects to walk for 30-60 sec at 1.25 m/s (2.8 mph) using their own prosthesis.

On Days 2, 3, or 4, we will ask subjects to walk at 1.25 m/s on a dual-belt force-measuring treadmill while we measure their metabolic rates, biomechanics, and muscle activity using their own passive-elastic prosthetic foot for:

- 1) 5 min with no visual feedback
- 2) 5 min with real-time visual feedback of affected leg (AL) peak propulsive force from the "no feedback" condition, and 5 min with no visual feedback
- 3) 5 min with real-time visual feedback of +20% greater AL peak propulsive force than the "no feedback" condition, and 5 min with no visual feedback
- 4) 5 min with real-time visual feedback of +40% greater AL peak propulsive force than the "no feedback" condition, and 5 min with no visual feedback
- 5) 5 min with real-time visual feedback of AL peak propulsive force and unaffected leg (UL) peak propulsive force, and 5 min with no visual feedback

On Days 2, 3, or 4, we will ask subjects to walk at 1.25 m/s on a dual-belt force-measuring treadmill while we measure their metabolic rates, biomechanics, and muscle activity using the emPOWER battery-powered ankle-foot prosthesis for:

- 1) 5 min with no visual feedback

- 2) 5 min with real-time visual feedback of AL peak propulsive force from the “no feedback” condition, and 5 min with no visual feedback
- 3) 5 min with real-time visual feedback of +20% greater AL peak propulsive force than the “no feedback” condition, and 5 min with no visual feedback
- 4) 5 min with real-time visual feedback of +40% greater AL peak propulsive force than the “no feedback” condition, and 5 min with no visual feedback
- 5) 5 min with real-time visual feedback of AL peak propulsive force and UL peak propulsive force, and 5 min with no visual feedback

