We will enforce 5 minutes of rest between trials. During the real-time visual feedback trials, we will ask subjects to match the power magnitude displayed on a computer screen placed in front of them with their AL and/or UL for those 5 minutes. Subjects will be asked to perform a maximum of 35 minutes of walking per day and each experimental session will require ~2 hours of time. The total time commitment for this study is approximately 8 hours; 2 hours per day over 4 days.

D. Description, Risks and Justification of Procedures and Data Collection Tools:

We propose to study healthy people who are familiar with using a prosthesis because this choice minimizes any potential confounding factors associated with novel prosthetic use. Walking requires low exercise intensity, yet poses no more than minimal cardiac risk for this population. We will restrict our patient age range to comply with the American College of Sports Medicine guidelines. The American College of Sports Medicine (ACSM) Guidelines for Exercise Testing and Prescription (Ninth edition, 2014) classify individuals of any age as having low or moderate risk to participate in an exercise program if they present no more than two of the following risk factors: males age \geq 45 yrs, females age \geq 55 yrs, first degree family history of coronary artery disease, cigarette smoking, sedentary lifestyle, obesity, hypertension, dyslipidemia (high cholesterol), and pre-diabetes. These guidelines further recommend that a medical exam and diagnostic exercise testing are not warranted prior to beginning a moderate exercise program for individuals at low to moderate risk. We are being conservative by including patients under 67 years of age (i.e. before their 67th birthday) who do not have any of the other risk factors listed above.

We will comply with Good Clinical Practices (GCPs) by upholding standards for the design, conduct, performance, monitoring, auditing, recording, analysis and reporting of our clinical studies, and by protecting the rights, safety, and well-being of human subjects. We will assure the quality, reliability, and integrity of data collected. We will maintain and monitor GCPs by obtaining Institutional Review Board (IRB)-approval, requiring informed consent, having a data-monitoring plan, reporting Adverse or Serious Adverse Events, having proper documentation, and validating our data collection and reporting procedures.

Foreseeable risks:

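### The order of feedback conditions 2–5, the prosthesis order and the split over days are not randomised or balanced; run as numbered, +40% is always trial 6 of 9

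*Combined protocol and SAP*

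**What the plan says.** Specific Aim 1 (Section I) has each subject walk "with no visual feedback, and then with real-time visual feedback targets of: 2) peak propulsive force from the" no-feedback trial, +20% and +40%, with symmetric feedback added as item 5. Aim 2 repeats this for the powered prosthesis.

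Section IV.B (Days 2, 3 and 4) gives one list per prosthesis: a no-feedback trial, then four numbered items, each a feedback trial followed by a 5-minute no-feedback trial. Item 4, for example, opens with "5 min with real-time visual feedback of +40% greater AL peak propulsive force than the" no-feedback level. Both lists are introduced by the same words: "On Days 2, 3, or 4, we will ask subjects to walk at 1.25 m/s on a dual-belt force-measuring treadmill". Each experimental day also has a short walk: "we will ask subjects to walk for 30-60 sec at 1.25 m/s (2.8 mph) using their own prosthesis". On spacing and load, the section says "We will enforce 5 minutes of rest between trials" and "Subjects will be asked to perform a maximum of 35 minutes of walking per day".

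Hypothesis 1b is that metabolic cost with the passive-elastic foot "will be lowest when subjects use visual feedback of +40% peak propulsive force compared to all other conditions"; Hypothesis 2b says the same for the powered device. Hypothesis 2c expects that, after a 5-minute rest, "subjects will retain the biomechanics resulting from the visual feedback conditions"; Hypothesis 1c expects no retention with the passive-elastic foot. Hypothesis 2d compares the two devices across all conditions.

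The only test named in Section IV.F is a paired t-test, used for power. Neither an allocation of order nor an order, period or day term appears anywhere.

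**The concern.** In a within-subject design, the order of conditions is what separates a condition effect from the passage of time. If all subjects follow one order, each condition has one position, and any trend over the session belongs equally to the condition and to its place in the list. Hypotheses 1b and 2b rest on one condition being lowest, so a trend could create the predicted pattern or hide it.

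The documents give reasons to take time effects seriously:

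- Hypothesis 2c predicts retention after a rest as long as the one between trials. If it is right, later powered-device trials inherit something from earlier ones.
- Section III reports that subjects walked differently with an earlier powered device by the final session although tuning, components and alignment were unchanged. Net prosthetic ankle work averaged 37% numerically lower on all slopes but one. That finding is biomechanical and between sessions, so it shows only that session can matter.

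The same logic applies to Hypothesis 2d. If one device tends to be tested first, or on particular days, its effect is mixed with order and day.

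**Working it through.** **Inputs.** Lists, trial length, rest and daily cap: Section IV.B. Hypotheses: Section I. Sample size 30 and paired t-test: Section IV.F. The plan gives no figure for order effects, so there is none to reproduce.

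**1. Positions if the list is run as numbered.** No feedback is trial 1; matched 2 (its no-feedback trial 3); +20% 4 (5); +40% 6 (7); symmetric 8 (9). Offsets of +40%: 6 − 1 = 5 against no feedback, 6 − 2 = 4 against matched, 6 − 4 = 2 against +20%, 6 − 8 = −2 against symmetric.

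**2. Time per day.** One list is 9 × 5 = 45 min against a cap of 35, so neither fits in one day. Both need 90 min and three days allow 3 × 35 = 105, so the plan is feasible. The split changes which trials share a day with their baseline. Keep each feedback trial with its following no-feedback trial as a pair (8 pairs in all):

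- Short walk not counted: 7 trials fit per day. A day with one baseline holds at most 3 pairs (1 + 6 = 7), so at least 8 − 6 = 2 pairs fall off their baseline day. Items 1–4 fill exactly 35 min, so +40% need not be displaced.
- Short walk counted: 6 trials fit per day, and all 18 trials must fill three days exactly. A day with one baseline plus pairs has an odd count, so both baselines share a day with 2 pairs, and exactly 6 of 8 pairs fall off it.

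The documents do not say which case applies.

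**3. Can the analysis repair a fixed order?** Take 30 subjects × 2 prostheses × 4 feedback conditions, with terms for subject, condition, prosthesis, position and day, three pairs on the baseline day and the fourth on a shared day. With one order for all, condition and position coincide and +40% minus matched is not estimable.

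The later no-feedback trials could be used to estimate a linear drift. The unadjusted per-subject variance of the contrast is 2σ². The offset is 4 trials, so the adjustment adds 4² divided by the sum of squared deviations of the trial positions used:

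- no retention, trials 1, 3, 5, 7, 9: 2 + 16/40 = 2.4σ²;
- equal retention after every condition, trials 3, 5, 7, 9: 2 + 16/20 = 2.8σ²;
- retention that differs by condition: not estimable.

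No such adjustment is planned.

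**4. Sensitivity to drift (assumption only).** The documents give no drift rate. If drift were 0.02, 0.05 or 0.10 SD of the paired difference per trial, with no true effect, a two-sided 5% paired t-test with n = 30 would reject for +40% against matched with probability 0.071, 0.185 or 0.563.

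**5. Balanced alternative.** Use sequences 2-3-5-4, 3-4-2-5, 4-5-3-2 and 5-2-4-3 at trials 2, 4, 6, 8. Each condition takes each position once and each ordered neighbour pair occurs once. With 8/7/8/7 subjects:

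- +40%: (8×8 + 7×4 + 8×2 + 7×6)/30 = 150/30 = 5.0;
- matched: (8×2 + 7×6 + 8×8 + 7×4)/30 = 150/30 = 5.0; the other two conditions also give 5.0.

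For other 8/8/7/7 arrangements the +40% against matched offset is at most 0.27; 8/7/7/8 gives (154 − 146)/30. In the model of step 3, with prosthesis order split 15/15, the pooled contrast is estimable, and position and day terms raise its variance by 0% (8/7/8/7) to 0.2%.

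Hypotheses 1b and 2b are prosthesis-specific. The pooled contrast has variance 2σ²/60 and the within-prosthesis contrast 2σ²/30, a factor of 2. A first-order carryover term adds about 9% to the pooled variance.

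**The case against.** The strongest reply is that the documents do not prescribe a fixed order. Only the no-feedback trial is placed by wording; numbers 2–5 may be labels, and the shared wording about Days 2, 3 or 4 is compatible with varied order. This stands. A reader might infer that Hypotheses 1b and 2b are already confounded, but the documents support only an unspecified order that becomes a confound if the list is followed.

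A second reply is that mitigation is built in. Feedback trials on one day are separated by rest, 5 minutes without feedback and rest, about 15 minutes in all, which may act as washout. Fasting, same time of day and subtraction of standing power reduce noise. These measures may shrink carryover, but they do not balance order. Extending Hypothesis 2c from biomechanics to metabolic cost is also conjecture.

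Two further inferences fail. One is that the bias favours +40%: learning and fatigue would act in opposite directions, and no drift rate is given. The other is that 45 minutes against a 35-minute cap makes the study infeasible: 90 of 105 minutes fit, and only the split is missing.

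Finally, balancing is only a partial remedy. Hypotheses 1b and 2b include the no-feedback comparison, whose offset falls only from 5 trials to a mean of 4.

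**Conclusion.** The concern holds as an omission with a conditional consequence. It is certain that condition order, prosthesis order and day split are neither randomised nor balanced in the documents. That all subjects follow the numbered order is inferred. On that assumption +40% sits 5, 4 and 2 trials after no feedback, matched and +20%, and 2 before symmetric. Its contrast with matched cannot be separated from position without assumptions about drift and retention that the plan does not make. The size and direction of any bias are unknown; the drift figures show sensitivity only. The omission should be fixed, because it bears on the contrasts in Hypotheses 1b, 2b and 2d and the change is cheap.

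**What to change.** - **Order.** Keep no feedback first, because it sets the targets. Randomise each subject to one of the four sequences above, in near-equal numbers among those enrolled, and randomise prosthesis order.
- **Analysis.** Prespecify a mixed model with condition, prosthesis, condition-by-prosthesis, sequence position and day, and subject as a random effect, so that Hypotheses 1b and 2b are tested within each prosthesis. Add a first-order carryover term as a sensitivity analysis.
- **Interpretation.** Treat contrasts among conditions 2–5 as order-protected. Report contrasts with no feedback with the caveat that a mean offset of 5 − 1 = 4 trials remains. Also report separately the subjects who receive bilateral +20% and +40% targets under Section IV.E (symmetry index below 5%), since those conditions mean something different for them.
- **Days.** Reconcile the lists in Section IV.B with the daily cap by stating which trials fall on which day and whether the 30–60 s walk counts.

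**Cost.** A randomisation list, a protocol paragraph and a written model; no extra subjects or walking. Some subjects meet +40% before +20%. If three pairs stay on the baseline day, the last condition falls on a later day: with 8/7/8/7 that is +40% for 8 of 30 subjects (27%), the same as matched, and about three quarters on average if the short walk counts. In that layout last position and the shared day coincide and share one term, but the condition and device contrasts stay estimable. Exact balance depends on the number of completers. If the team already randomises, the order paragraph need only record it.

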Unified deformable (UD) segment analysis. We will use a UD segment analysis to determine the mechanical power derived from the prosthesis plus the residual shank due to elastic energy storage and return [16]. We will develop a model of each prosthesis as a UD segment to characterize the limb-to-ground interaction during walking. The UD segment power analysis is a mathematical algorithm that synthesizes force and displacement in a shank-based reference frame to quantify the rate of prosthetic energy stored and returned. This analysis does not require an 'ankle' joint to be defined, and thus is well-suited to quantify passive-elastic prosthetic foot mechanics. The UD analysis will allow precise measurement of how changes to the use of passive-elastic or battery-powered ankle-foot prostheses affect overall prosthetic function; in particular, the magnitude of prosthetic energy storage and return during walking. These analyses will help identify causal relationships between prosthetic mechanics and overall walking performance for Veterans with TTAs [16].

Symmetry Index (SI). We will calculate the absolute value of the symmetry index [17-19], which is expressed as a percentage, to establish the magnitude of asymmetry between the AL and UL for

each biomechanical variable (var):
$$SI = \left| \frac{var_{UL} - var_{AL}}{0.5(var_{UL} + var_{AL})} \right| \times 100$$
. These variables will include 3D joint range of motion, peak moment, peak power, net mechanical work, stiffness, and UD power, as

well as peak and stance-average GRFs, individual leg mechanical work, and kinematic timing for each leg.

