We have a few potential limitations that could affect the proposed project. Previous studies have found that peak propulsive force is 23-36% lower in the AL when people with a TTA use a passive-elastic prosthesis and is 15-28% lower in the AL when people with a TTA use a powered ankle-foot prosthesis compared to non-amputees [14]. Though it's unlikely, it is conceivable that a subject could elicit more symmetric peak propulsive GRFs. If we find that a subject has a symmetry index for peak propulsive force that is less than 5% during the initial "no feedback" walking trial, we will provide visual feedback of peak propulsive GRFs from both legs at +20% and +40% compared to "no feedback" and will compare the results from these subjects with the overall results from all subjects. It is possible that we will not find significant differences in biomechanics, metabolic costs, or muscle activity with use of targeted visual feedback training of peak propulsive force. However, peak propulsive force has a strong influence on step-to-step transition work and the metabolic cost of walking; therefore, we believe that there will be a significant beneficial effect of real-time visual feedback training. It is also possible that there would be no significant differences between use of passive-elastic versus battery-powered ankle-foot prostheses, but this seems highly unlikely based on previous studies that have compared the use of passive-elastic prosthetic feet to battery-powered ankle-foot prostheses and found significant differences in metabolic cost of transport, step-to-step transition work, and preferred walking speed [11, 14, 23, 24]. Further, though there may be small differences between walking on a treadmill and over-ground walking, we chose to have participants perform experimental trials on a treadmill, which will allow us to control speed while we measure multiple consecutive strides and steady-state metabolic rates, while providing targeted real-time visual feedback. We will then use the results from a treadmill and computer monitor to inform future prosthetic designs that could use a different type of feedback, such as vibration or sound, to provide feedback in a real-world setting. No procedures, situations, or materials are considered to be hazardous to personnel. In addition to improving prosthetic rehabilitation and function, our results could inform the design and control of lower limb prostheses.

F. Data Analysis Plan:

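### In the affected-leg-only +20% and +40% trials, the symmetry index for peak propulsive force is largely set by the target, so it should serve as a manipulation and overshoot check, not as a test of H2a or H2d

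*Combined protocol and SAP*

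**What the plan says.** Section IV.A (Symmetry Index) defines SI as the absolute difference between UL and AL, divided by their mean, times 100: "We will calculate the absolute value of the symmetry index [17-19], which is expressed as a percentage". Its stated purpose is "to establish the magnitude of asymmetry between the AL and UL for" every gait variable analysed, and the list includes joint measures "well as peak and stance-average GRFs, individual leg mechanical work, and kinematic timing for each leg". Peak propulsive force is thus one of the variables scored.

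Section IV.B (Days 2, 3 and 4) sets the feedback targets. One reads "5 min with real-time visual feedback of +40% greater AL peak propulsive force than the" no-feedback trial, and the +20% trial has the same form. The UL has no target in either. A fifth condition shows the forces of both legs, and Specific Aims 1 and 2 describe it as matching symmetric forces.

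Under Specific Aim 2, H2a predicts that powered-foot users will match the +20%, +40% and symmetric targets without compensation, "which will improve symmetry between legs and dynamic stability". H2d predicts "more symmetric biomechanics, lower metabolic costs, and improved dynamic stability when using powered compared to passive-elastic prostheses across all conditions". Neither exempts the force being fed back.

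Section IV.E reports from earlier work, for the passive foot, that "peak propulsive force is 23-36% lower in the AL when people with a TTA use a passive-elastic prosthesis", with non-amputees as the reference. For the powered foot it says that the same force "is 15-28% lower in the AL when people with a TTA use a powered ankle-foot prosthesis compared to non-amputees". The section contains the only safeguard: subjects whose no-feedback SI for this force is below 5% receive +20% and +40% targets for both legs, and their results are compared with those of all subjects.

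The plan gives no signed index and no rule for overshoot. It does not say whether propulsive-force SI in the AL-only trials tests H2a and H2d or only shows that the target was met.

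**The concern.** A subject who matches the +40% target multiplies AL force by 1.4. Whether that ends below, at or above UL force depends on the starting deficit. An unsigned SI gives the same score to an AL that still falls short and to one that has gone equally far past.

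Both devices get the same multiplier, so the device with the smaller starting deficit overshoots sooner. The powered foot could score as less symmetric than the passive foot at +40% because it began closer to symmetry. A subject who starts fairly symmetric and complies fully could score as worse than at baseline. For this one variable, the answers to H2a and H2d in the AL-only trials would then largely reflect the choice of target and not a benefit of the device or the training.

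**Working it through.** **The plan's own figure.** Section IV.F, Table 1, gives power of 0.717-1.0 for SI of peak propulsive force (paired t-test, n = 30, α = 0.05). It cannot be reproduced, because no mean difference or SD is given. A power of 0.717 corresponds to a standardised paired difference of 0.479 if two-sided. Nothing below rests on it.

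**Inputs.** AL deficits *d* relative to non-amputees (IV.E): powered 15-28%, midpoint 21.5%; passive 23-36%, midpoint 29.5%. Multipliers *k* = 1, 1.2 and 1.4 (IV.B). Assumptions: UL force is *u* times the non-amputee level, the same for both devices and unchanged during the trial; targets are matched exactly. The base case is *u* = 1.

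**Formulas.** r = AL/UL = (1 − d)/u, and |SI| = |1 − kr| / [0.5(1 + kr)] × 100.

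**Example.** Powered, d = 15%, +40%: kr = 1.4 × 0.85 = 1.19, so |SI| = 0.19/1.095 × 100 = 17.4%.

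| Device, deficit | r | No feedback | +20% | +40% | AL/UL at +40% |
|---|---|---|---|---|---|
| Powered, 28% | 0.720 | 32.6 | 14.6 | 0.8 | 1.008 |
| Powered, 21.5% | 0.785 | 24.1 | 6.0 | 9.4 | 1.099 |
| Powered, 15% | 0.850 | 16.2 | 2.0 | 17.4 | 1.190 |
| Passive, 36% | 0.640 | 43.9 | 26.2 | 11.0 | 0.896 |
| Passive, 29.5% | 0.705 | 34.6 | 16.7 | 1.3 | 0.987 |
| Passive, 23% | 0.770 | 26.0 | 7.9 | 7.5 | 1.078 |

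**H2d at +40%.** Like ends paired, powered versus passive: midpoints 9.4 v 1.3 and shallow ends 17.4 v 7.5 (both against H2d); deep ends 0.8 v 11.0 (in line). With no feedback, powered is better in all three pairings.

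Because |SI| is the same for a ratio and its reciprocal, powered scores worse when (1.4 r_powered)(1.4 r_passive) > 1, that is, when the product of the baseline ratios exceeds 1/1.96 = 0.510.
- Midpoints: 0.785 × 0.705 = 0.553. The reversal lasts while u < √(0.553/0.510) = 1.04.
- Shallow ends: 0.85 × 0.77 = 0.655. It lasts while u < √(0.655/0.510) = 1.13.
- Deep ends: 0.72 × 0.64 = 0.461. No reversal at u = 1.

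**H2a against no feedback.** Scaling by k worsens |SI| when r > 1/√k.
- +40%: r > 0.845, a deficit below 15.5% of UL, baseline SI below 16.8%.
- +20%: r > 0.913, baseline SI below 9.1%.

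In addition, +40% scores worse than +20% when r > 1/√1.68 = 0.772, a deficit below 22.8%.

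**Safeguard.** SI = 5% is r = 1.95/2.05 = 0.951. At that point +40% gives kr = 1.332 and |SI| = 28.5%. Subjects with baseline SI of 5-16.8% keep the AL-only target and, on these assumptions, end with a larger |SI|.

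**Sensitivity of the powered foot at +40%.**
- u = 0.90: AL/UL 1.12-1.32; at the shallow end |SI| goes from 5.7 to 27.8.
- u = 1.10: AL/UL 0.92-1.08; |SI| improves on no feedback at both ends.
- u = 1.20: AL/UL 0.84-0.99; no crossing.

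**The case against.** The index does what it is meant to do. An AL 19% above the UL is real asymmetry, and an unsigned SI gives its size correctly. This stands. The difficulty lies in pairing an AL-only multiplier with a hypothesis that matching it improves symmetry, while the index hides direction.

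Passing symmetry is also not the same as worse symmetry. At the three powered deficits in the table, +20% always improves |SI|, and +40% improves it at 28% and 21.5%. Only the last half point of the quoted range falls below 15.5%. This stands too.

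Replacing the unsigned index with a signed one would do harm. In the symmetric-feedback condition errors can fall either way: half the subjects at +10% and half at −10% average to zero, which looks like perfect symmetry. The signed index therefore belongs beside the unsigned one.

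Finally, the scope is narrow. H2a and H2d cover many variables, the fifth condition targets symmetry directly, and direction can be recovered from data already planned. H1a confines its asymmetry prediction to variables other than the fed-back force, so one could read that force as the manipulated variable throughout. H2a and H2d do not say so, however, and SI of this force has its own line in the power table. The rule of interpretation is still missing.

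**Conclusion.** The point holds for peak propulsive force in the AL-only trials. There |SI| is largely determined by the target and the starting deficit, and it mixes residual deficit with overshoot. With UL at the non-amputee level and unchanged and targets matched exactly, the powered AL/UL ratio at +40% is 1.01-1.19. The device comparison then runs against H2d at the midpoints and shallow ends of the quoted deficits, but not at the deep ends. The midpoint reversal goes once UL is more than about 4% above non-amputees, and the shallow-end reversal above about 13%. For H2a at +40%, the exposed group is subjects with baseline SI of 5-16.8%.

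A reader might infer that most powered-foot users will end less symmetric, or that H2a will be reversed overall. The documents do not support that. The deficits are relative to non-amputees and not to the subject's own UL, no between-subject SD is given, and the quoted range does not say whether it spans subjects or conditions. If the AL/UL ratio is assumed normal about the powered midpoint with SD 0.05-0.15, and subjects under 5% are excluded, 65-92% would pass symmetry at +40% but only 11-27% would score worse than with no feedback. Those shares depend on the assumed SD.

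**What to change.** In the Symmetry Index paragraph and the Data Analysis Plan:
- Keep |SI| as the measure of the size of asymmetry.
- For peak propulsive force, report beside it the signed SI, (UL − AL)/[0.5(UL + AL)] × 100, or the AL/UL ratio, with the number of subjects whose sign reverses.
- State in advance that propulsive-force SI in the AL-only +20% and +40% conditions is a manipulation and overshoot check, not a test of H2a or H2d.
- Take the propulsive-force symmetry claim from |SI| in the no-feedback and symmetric-feedback conditions.

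Other variables stay as planned. The change is to wording and analysis only and needs no new data or procedures. The cost is that the symmetry claim for this one variable covers fewer conditions.
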